5.3.1 Allowed Interventions

See 5.3.

5.3.2 Required Interventions

None

5.3.3 Prohibited Interventions

1) Prior experience with Yoga and/or CBT (more than 5 Yoga classes or CBT sessions within the last 3 years)

2) Current practice of mind-body techniques (e.g., yoga, meditation, Tai-Chi, etc) or CBT3) Also prohibited is any concomitant psychotherapy for GAD.

4) Initiation of anxiolytic pharmacotherapy during the 12 session treatment period is not allowed (see 8.0 exception under Intervention Discontinuation)

5.4 Adherence Assessment

Monthly reports will monitor subject enrollment, completion, attrition, and individual subject progress as well as the completion of critical assessments. Additional reports will be done as needed to monitor baseline characteristics, protocol adherence, and other issues of interest.

Treatment integrity will be insured through careful supervision and adherence monitoring of all three interventions (see above Treatment Fidelity).Patient adherence will be measured by session attendance, and the Homework Compliance Scale. The working alliance inventory will also be assessed. Based on the available data, non-adherence to CBT, yoga, and SE instructions are unlikely to be of great concern. In fact, patients are likely to be highly motivated to practice strategies that may result in immediate relief of their suffering without experiencing any unpleasant side effects. Nevertheless, patient adherence will be considered as a moderator in the final analysis. Binary adherence will be defined as for use in the per protocol analysis as attending at least 10 of the 12 group treatment sessions in addition to a score of at least 4 on the homework compliance scale (higher than moderate compliance of 3) out of a scale of 0-6.

6. STUDY PROCEDURES

6.1. Schedule of Evaluations

Form Type	Measure	Admin By	Mo. -1 (Scree n*)	Wk 0 (Baseline)	Wks 1-5	Wk 6 (Mid Tx)	Wks 7-11	Wk 12-13 (Post Tx)	Wk 36-37 (6 mo. FU)
Diagnosis & Screening	Eligib ility/Informed Consent	IE + RA pre- screen	Х						
	SCID/ADIS-5	IE	Х						
	CGI-S/CGI-I ^{1,} 2	IE	Х	Х	X (biweekly)	Х	X (biweekly)	Х	Х
	SIGH-A	IE	Х	Х	(orweekiy)	Х		Х	Х
	Demographics	Self	Х						
	Medical History	MD/RN	Х						
	Screening Medications/T herapy Log	MD/RN	Х						
	Physical Exam	MD/RN	Х						
	MoCA	MD/RN	Х						
Secondary	STAI	Self		Х		Х		Х	Х
Outcomes	BAI	Self		Х	X X (biweekly)	X (biweekly)	Х	Х	
	BDI-II	Self	Х	Х	(;))	Х	())	Х	Х
	PSS	Self		Х		Х		Х	Х
	WHOQOL- BREF	Self		Х		Х	Х	Х	
	SCL-90	Self		Х		Х		Х	Х
	PSWQ	Self		Х	X (weekly if in CBT)	Х	X (weekly if in CBT	Х	Х
	ISI	Self		Х	,			Х	
	PSQI	Self		Х				Х	
	SOCI	Self						Х	
	ASQ	Self		Х		Х		Х	Х
Mediators	MCQ	Self		Х		Х		Х	Х
	FFMQ	Self		Х		Х		Х	Х
Psycho-	ECG (RSA)	RA		Х		Х		Х	Х
physiological & Biological	Salivette Sample	Self		Х		Х		Х	Х
stress	Affect Grid	RA		Х		Х		Х	Х
	Vital Signs	RA		Х		Х		Х	Х
Tx Details	Credibility / Expectancy	Self		Х		Х		Х	Х
	Homework compliance	Self			X (weekly)	Х	X (weekly)	Х	
Safety & Integrity	Adverse Events Log ³	RA		Х	X (weekly)	Х	X (weekly)	Х	Х

	Concomitant Medications/T herapy Log ³	RA		Х	X (weekly)	Х	X (weekly)	Х	Х
	Suicidality checklist ²	IE	Х	Х	X (biweekly)	Х	X (biweekly)	Х	Х
	Working alliance	Self			(0111001115)	Х	(011100111))	Х	
	SAFETY Form	RA		Х	X (weekly)	Х	X (weekly)	Х	Х
	End of Study	RA			Compl	eted afte	er 6-month FU/ear	ly termination	on visit
	Protocol Deviations	RA					Ad hoc, as needed	ed	
Quality Assurance	Adherence/ Competence	Fidelity rater			20% of s	essions (per schedule sent	by study sta	tistician)
	Inter-rater Reliability	IE		15% of sessions (per schedule sent by study statist					tistician)

*Data collected during the screening is part of routine clinical care; Wk=Week; Mo=Month; FU=Follow-up; Tx=Treatment; IE=Independent Evaluator; MD/RN=Physician/Nurse; ¹The CGI-I will not be administered at the screening or baseline, as it captures post-baseline improvement; ²Administered weekly if the CGI-I≥5 at any time; ³Information gathered by the RA will be reviewed by the therapist/instructor prior to each weekly class.

6.2 **Description of Evaluations** Assessment Instruments and Procedures

All clinician-rated outcomes will be assessed by Independent Evaluators (IEs) blind to treatment assignment. The IEs will be M.D., Ph.D., or experienced Masters-level diagnosticians with previous research experience with structured interviewing who will receive additional training and certification for this study under the direction of Drs. Simon and [name] with certification by [name]. Any new raters will undergo training including rating at least 2 audio or videotaped interviews then have 2 interviews taped and reviewed for agreement by an expert rater. In addition to the training procedures, study staff will hold weekly meetings during which all initial diagnostic interviews conducted that week are discussed in the presence of senior clinicians, and in the instance of diagnostic disagreement, the sources of these differences are reviewed and a consensus diagnosis is reached. The staff meeting should also reduce the potential for interviewer drift. A two-level system will be used to maintain the reliability of diagnoses and of other clinical ratings in the study, consisting of weekly supervision and ongoing rating of selected clinical assessments, which will all be digitally recorded. Each month, an independent evaluator (IE) will listen to an assessment performed by another IE associated with the study and independently complete the assessment instruments. These duplicate ratings will be used both to calculate kappa coefficients and for supervision. Differences between raters will be discussed during supervision to identify reasons for disagreement and improve inter-rater reliability. These procedures will help us ensure that IEs refine their diagnostic skills and will also establish common guidelines for ongoing use in diagnostic decision-making. Inter-rater agreement will be assessed via evaluation of digital recordings of diagnostic interviews.

Interview-Based Measures

Structured Diagnostic Interview (SCID): The Structured Clinical Interview for DSM-IV (SCID-IV: will be updated to SCID5 as soon as available, anticipated prior to enrollment) will be administered at MGH CATSD to determine the absence of diagnostic exclusion criteria and assess co-occurring psychiatric disorders. The Anxiety Disorders Interview Schedule for DSM-5 (ADIS-5; [92]) will be used at BU to determine DSM-5 psychiatric diagnoses (please note that the ADIS-5 was developed at the Center for Anxiety and Related Disorders at Boston University, therefore, this interview is already available to us).

Each principal investigator has extensive experience with diagnostic interviews, and all raters will be certified. Cross site certifications and quality assurance ratings will occur to assure rating consistency of diagnoses as administered in the SCID with the ADIS, an overlapping interview.

Clinical Global Impression of Severity (CGI-S; [94-97]): This is a 1-item scale asking the investigator to assess the patient's overall level of illness severity. The clinician should integrate all aspects of the patient's condition when using this scale. It will be used at assessments.

Clinical Global Impression of Improvement (CGI-I; [93]): This 1-item instrument allows evaluators to give an overall rating to subject's level of improvement or worsening on a scale of 1-7, with 1 correlating to very much improved and 7 correlating to very much worse. It will be used at assessments.

Structured Interview Guide for the Hamilton Anxiety Rating Scale (SIGH-A; [98]) This 19-item structured, clinician-administered rating scale provides an overall measure of anxiety. It will be used at assessments.

Self-Report Measures

Demographics Form: Patients will be asked to fill out a questionnaire regarding age, race, ethnicity, gender, socioeconomic status in addition to their religious beliefs and practices.

State-Trait Anxiety Inventory (STAI; [100]): The STAI-A is a 40-item, multiple-choice questionnaire that differentiates between the temporary condition of "state anxiety" and the more general and long-standing quality of "trait anxiety." As a result, it is useful in both clinical and research contexts. It will be used at assessments.

Beck Anxiety Inventory (BAI; [101]): This 21-item self-report inventory designed to measure severity of anxiety symptoms in psychiatric populations has high internal consistency and test-retest reliability. It will be used at assessments.

Beck Depression Inventory (BDI-II; [102]): This 21-item self-report inventory designed to measure severity of depression symptoms in psychiatric populations has high internal consistency and test-retest reliability. It will be used at assessments.

Perceived Stress Scale (PSS; [84]): This 10-item scale is the most widely used psychological instrument for measuring the perception of stress. It is a measure of the degree to which situations in one's life are appraised as stressful. It will be used at assessments.

Symptom Checklist 90 (SCL-90; [87]): This is a 90-item instrument used to assess to what degree certain problems and complaints bothered or distressed an individual during the past week. It will be used at assessments.

Quality of Life Scale (WHOQOL-BREF; [103]): This instrument assesses quality of life enjoyment and satisfaction. It will be used at assessments.

Meta-cognition Questionnaire (MCQ; [106]): This is a 65-item instrument used to assess beliefs people have about their thinking. It will be used at assessments.

Five-Facet Mindfulness Questionnaire (FFMQ; [104,105]): This scale has recently been developed to measure trait-like aspects of six sub-factors: observing/noticing experience; acting with awareness, avoiding "auto pilot"; describing/labeling; non-judging of self-experience; non-reacting to internal experience; kindness/compassion/friendliness. The factor structure of this scale has been validated. It will be used at assessments.

Penn State Worry Questionnaire-Past Week (PSWQ-PW; [107]): This is a 15-item, self-report measure of worry (PSWQ) Items are rated on a five-point Likert scale, and are summed to form a total score ranging from 16 to 80. The PSWQ has excellent psychometric properties in student, community, and clinical samples. It will be used at assessments.

Pittsburgh Sleep Quality Index (PSQI; [140]): This is a 19-item, self report measure of sleep quality over a one month duration. The items make up seven different component scores consisting of sleep quality, sleep latency, sleep duration, habitual sleep efficiency, sleep disturbances, use of sleep medication and daytime dysfunction. This measure also generates a global sleep quality score. It will be used at assessments.

Insomnia Severity Index (ISI; [141]): This is a 7-item, self-report measure to assess insomnia as defined by the DSM-IV. It will be used at assessments.

Affective Style Questionnaire (ASQ; [142]): This is a 20-item, self report measure to assess individual differences in emotion regulation.

Social Identification Scale (SOCI; [143]): A 11-item, self report measure to assess social identification with the treatment group in order to determine if social identification is a potential confounder or effect modifier for our primary and secondary outcomes.

Psychophysiological/Biological Measures of Stress

Endocrinological Stress Measure (Cortisol). Following the methodology by Vreeburg et al. [108], we will measure the salivary cortisol awakening response at each assessment point. Subjects will collect saliva samples using Salivettes (Sarstedt) at home on a regular working day representative of their regular sleep/wake schedule at 4 time points (at habitual wake time and at 30, 45 and 60 minutes later) and will return the samples to the investigators. Cortisol analysis will be performed by competitive electrochemiluminescence immunoassay using standard

procedures; the functional detection limit is 2.0 nmol/L and the intra and inter-assay variability coefficients in the measuring range are <10%. All 4morning salivary cortisol values will be used to calculate the area under the curve as a measure of the dynamic of the cortisol awakening response, which will be evaluated before and after the three treatments. Cortisol analyses will include covariates for smoking status and oral contraceptive use.

We will measure cardiac vagal tone by recording respiratory sinus arrhythmia (RSA). RSA refers to the rhythmic variations in heart rate that occur at the frequency of respiration, and reflects parasympathetic control over the heart (e.g., Berntson, Cacioppo, & Quigley, 1993). To measure breathing, a flexible respiration band will be strapped around subjects' chest. A software program computes RSA using the peak-valley method (Grossman, 1983). This method derives RSA by calculating the difference between the minimum interbeat interval during inspiration and the maximum interbeat interval during expiration. [127-134].

Treatment Moderator Measure

Credibility/Expectancy Questionnaire: This questionnaire is used to examine whether credibility and expectancy moderates therapy outcome.

Study Integrity and Safety Measures

Montreal Cognitive Assessment (MoCA; [113]): This is a 10-item rapid screening instrument for mild cognitive dysfunction. It assesses different cognitive domains: attention and concentration, executive functions, memory, language, visuoconstructional skills, conceptual thinking, calculations, and orientation. This measure will be used to assess entry criteria.

Homework Compliance Scale[110, 111]: This is a 1-item clinician-rated instrument. It assesses homework compliance and will be administered prior to each session.

Working Alliance Inventory (Short Form; [112]): This is a 12-item self-report instrument. It assesses the working alliance and will be administered prior to each session.

Adverse Events Monitoring Form: Adverse events will be assessed at each visit. Adverse events will be rated as mild (noted change in the subject's condition that causes minor distress and does not affect activity), moderate (notable distress and/or mild disruption in usual activity), or severe (marked distress and/or major disruption in usual activity).

Concomitant Medications: *Concomitant medication* is defined as any medication taken on or after the start of double-blind investigational product. Concomitant drug use will be summarized by the number and proportion of patients in each treatment group receiving each drug within each therapeutic class. Multiple drug use by a patient will be counted only once.

Medical Review Form: A study nurse with MD oversight or physician will assess physical fitness with the medical history form and a standard physical exam, emphasizing musculoskeletal, neurologic, and cardiac history. Participants' current health status, medical

history, past surgeries, and past psychiatric medication use will be assessed. Pregnancy will be assessed by a urine pregnancy test at the screen for women of childbearing age.

6.2.1. Screening Evaluation.

Individuals who contact the Center will be screened initially by phone for interest in the proposed research, as well as general diagnostic and study eligibility, and interest in research participation. Data for participants who undergo the phone screening process will be deidentified and recorded in the study database phone screening log. Reasons for ineligibility and for non-participation of eligible subjects will be recorded.

Interested patients who are eligible for participation will be scheduled for an evaluation meeting where informed consent will be obtained.

Consent: The consent process will be conducted by an experienced member of the study and staff. All potential participants will review the consent form, risks, and benefits associated with the protocol with an approved study investigator and will sign consent prior to completion of any study assessments in this protocol. The study investigator will explain the study, answer any questions, and obtain written informed consent. Participants will be given as much time as needed to review the consent and ask questions prior to participation in study procedures. The study procedures and consent form will be approved by the Institutional Review Board at each of the enrolling sites prior to study initiation. There will be a single informed consent form at each enrolling site that describes both the assessment and study procedures.

We will allow a maximum of one month for the time between baseline assessment of participants and randomization. For any participant for whom completing the screening process is delayed, with PI approval baseline measures will be repeated prior to entry. Once participants complete eligibility and are randomized to a group, they will start treatment within 4 weeks.

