Yoga for generalized anxiety disorder: A comparison between yoga, cognitive behavioral therapy, and stress education training

Objectives

The general purpose of the study is to determine whether yoga is an effective method for treating GAD, and its relative efficacy compared to a standard psychosocial intervention. Our primary objective is to examine the short-term treatment efficacy of yoga on GAD symptoms. Our secondary objective is to examine the long-term treatment efficacy of yoga on GAD symptoms. Our tertiary objective is to examine and compare the mechanism of treatment changes in yoga and traditional CBT for GAD.

Design and Outcomes

This five-year multi-site study will examine the comparative efficacy of yoga, CBT, and stress education, a previously employed control condition, for patients with GAD. Across 2 enrolling centers (BU and MGH) we will randomize 230 patients with GAD to one of three 12 session weekly study treatments: 12-weekly yoga (n=95), CBT (n=95), or stress education (SE: n=40). Independent clinical assessments will occur before the 12-session intervention phase, at mid-treatment, after the intervention, and at 6-month follow-up. All clinician-rated outcomes will be assessed by trained Independent Evaluators (IEs) blind to treatment assignment. Response (CGI-I of 1 or 2) will serve as the primary outcome measure alongside the SIGH A as the core secondary continuous measure. Secondary outcome measures also include the STAI, PSS, BDI-II and BAI, QOL, ISI, PSQI and PSWQ. The FFMQ, MCQ, pre-ejection period, and cortisol are examined as possible mediators of change. The Credibility/Expectancy Questionnaire will be administered to examine whether credibility and expectancy moderates therapy outcome. In addition, we will explore whether clinical characteristics (comorbid diagnoses) and demographic characteristics (age, sex, SES) are possible moderators. We hypothesize that Yoga and CBT will each be superior to SE at post-treatment FU, and Yoga and CBT will not differ based on equivalency analyses. We predict that treatment changes during yoga are mediated via changes in mindfulness and changes in vagal tone, whereas changes in CBT are mediated via changes in maladaptive cognitions.

Interventions and Duration

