1.2. Secondary Objectives

Specific Aim 3: Mediation Analyses. Our tertiary aim is to examine and compare the mechanism of treatment changes in yoga and traditional CBT for GAD. We predict that treatment changes in responder rates during yoga treatment will be mediated via changes in mindfulness and changes in vagal tone (Hypothesis 3.1), whereas changes in CBT will be mediated via changes in maladaptive cognitions (Hypothesis 3.2.). Moderators of "responder rates" will also be examined.

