Audio CD's will be provided to guide subjects through daily home practices throughout the 12-week intervention to achieve mastery and self-efficacy. The 20-minute session will begin with spinal flexibility and loosening for a physical release of tension and increased body awareness. Subjects will then practice a breathing meditation specifically recommended for coping with anxiety. In general yoga and meditation home practice compliance is reported as being feasible and equivalent to that of other behavioral interventions [74, 90, 91]. [name], a co-investigator on this study, has observed compliance in a home yoga intervention averaging 29 minutes of a daily assigned 45-minute intervention (unpublished data). We believe that we will observe adequate compliance from the proposed home intervention, and with more rigorous follow-up to encourage adherence, and expect better compliance than in our pilot trial (see preliminary data above.)

Stress Education Group (SE): SE will also include 12 weeks of group and home practice sessions. SE will control for attention from instructors, expectancy effects, and group support effects, Stress Education (SE) will be employed as an active control intervention. SE is currently used in NIH-funded protocols at the *Benson-Henry Institute for Mind-Body Medicine* at MGH. In this condition, participants will be provided with detailed and extensive information about stress and health, but will not receive any CBT, yoga, or other mind-body training techniques. Content areas will include definitions of stress and the stress response, the fight or flight response, physiological and psychological effects of stress, stress and performance, the negative stress cycle, stress and health/illness, stress and immunity, stress buffers, stress hardiness, stress and heart disease, the role of genes and environment in health, the contribution of lifestyle behaviors such as caffeine and alcohol intake and cigarette smoking, and the importance of regular exercise and proper diet (without specific instructions for exercise or dietary changes). For the daily 20 minute home practice subjects will listen to SE audio CDs containing information about nutrition

and positive perspectives on lifestyle and emotions. Therefore, we believe that comparable social and attention controls will be placed in the SE group.

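### Vagal tone as a mediator of yoga is measured by peak-valley RSA with no breathing term, so Hypothesis 3.1 needs a pre-specified analysis with and without breathing

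*Combined protocol and SAP*

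**What the plan says.** **The hypothesis.** Section 1.2, repeated in 9.1, predicts that response to yoga will be "mediated via changes in mindfulness and changes in vagal tone (Hypothesis 3.1").

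**The measure.** Sections 2.2 and 6.2 describe it identically: "We will measure cardiac vagal tone by recording respiratory sinus arrhythmia (RSA"). On scoring: "A software program computes RSA using the peak-valley method". The score is obtained by "calculating the difference between the minimum interbeat interval during inspiration and the maximum interbeat interval during expiration". On respiration: "To measure breathing, a flexible respiration band will be strapped around subjects' chest". The only use described for the breathing signal is to compute RSA. The documents do not mention breathing rate or depth, paced breathing, or the condition under which the recording is made. Section 6.1 schedules ECG (RSA) at baseline, week 6, post-treatment and 6-month follow-up.

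**The model.** Section 9.6 uses three mediators: mindfulness, vagal tone and maladaptive cognitions. The a paths (yoga vs SE and CBT vs SE on each mediator) come from mixed models. The b paths come from the response GLMM with all three mediators entered together. Follow-up data are excluded. The covariates for all analyses are demographics and comorbid diagnoses. Cortisol has its own list in section 6.2: "Cortisol analyses will include covariates for smoking status and oral contraceptive use". RSA has none.

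**The arms.** Section 5.1 puts breathing techniques in every yoga class. On daily home practice it says: "Subjects will then practice a breathing meditation specifically recommended for coping with anxiety". The same section says that SE participants receive no mind-body training.

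**The Précis.** "The FFMQ, MCQ, pre-ejection period, and cortisol are examined as possible mediators of change". RSA is not in that list. Section 9.5.2 has RSA where the Précis has pre-ejection period, and the schedule in 6.1 contains ECG (RSA) but no pre-ejection period measure.

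**The concern.** RSA is a heart-rate swing tied to the breath, and the peak-valley score is taken within each breath. If that score depends on how slowly or deeply a person breathes as well as on vagal control, the yoga vs SE contrast on RSA mixes two things: a change in breathing pattern and a change in vagal tone. Randomisation does not separate them, because breathing is something that yoga trains and SE does not.

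At stake is the label on the mediated pathway. The trial could report that yoga works through vagal tone when the recording shows only that yoga participants breathe differently. The distinction matters to the plan itself. Section 2.2 treats breathing regulation and the vagal system as different links in the proposed mechanism, looks ahead to dismantling studies of breath regulation, and wants the biomarker data to guide that later work.

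**Working it through.** **1. The plan's own figure.** Section 9.2 states mediation power above .81, with large a paths and medium b paths given in words only. This point does not dispute that figure. As a plausibility check, take d = 0.8 for the a path with 95 yoga and 40 SE participants: two-sided power is 0.989. A simulation of 230 patients (95/95/40), requiring both a (linear model) and b (logistic model) to be significant at two-sided 0.05, gives joint power of about 0.79, 0.95 and 0.99 at b odds ratios of 1.5, 1.7 and 2.48 per SD. The stated figure is plausible. It cannot be reproduced exactly without numerical effect sizes.

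**2. How far breathing rate alone might move RSA (assumed model).** The documents give no figure. Assume constant depth and amplitude proportional to 1/√(1 + (f/fc)²), where f is breaths per minute divided by 60 and the corner fc lies between 0.10 and 0.20 Hz. Then 15, 12 and 10 breaths/min are 0.250, 0.200 and 0.167 Hz. For fc = 0.10, slowing from 15 to 12 gives √(1 + 6.25)/√(1 + 4) = 2.693/2.236 = 1.204.

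| fc (Hz) | 15 to 12 breaths/min | 15 to 10 breaths/min |
|---|---|---|
| 0.10 | +20.4% | +38.5% |
| 0.15 | +16.6% | +30.0% |
| 0.20 | +13.2% | +23.0% |

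These percentages cannot be turned into an a-path effect size, because the documents give no standard deviation for RSA.

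**3. When a breathing change becomes false mediation (assumed inputs).** Same 95/95/40 layout, 1,500 runs per cell, one time point. True vagal tone has no treatment effect and no effect on response. Yoga slows breathing by 0.5 or 0.8 SD. RSA correlates 0.3, 0.5 or 0.7 with slow breathing within arm, so the yoga arm's RSA shifts by the product, from 0.15 SD (0.5 × 0.3) to 0.56 SD (0.8 × 0.7). Slow breathing predicts response at an odds ratio (OR) of 1.0, 1.5 or 2.0 per SD. False mediation means that both paths are significant.

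| Slowing (SD) | Correlation | a path significant | False mediation, OR 1.0 | OR 1.5 | OR 2.0 |
|---|---|---|---|---|---|
| 0.5 | 0.3 | 10.6–13.1% | 0.5% | 1.5% | 3.7% |
| 0.5 | 0.5 | 26.5–28.6% | 1.3% | 8.1% | 17.4% |
| 0.5 | 0.7 | 44.3–47.6% | 2.4% | 22.8% | 39.9% |
| 0.8 | 0.3 | 24.9–26.1% | 1.3% | 3.4% | 8.1% |
| 0.8 | 0.5 | 55.5–57.1% | 2.7% | 15.8% | 35.0% |
| 0.8 | 0.7 | 84.5–85.9% | 3.9% | 46.5% | 77.6% |

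With breathing added to both models, the false-mediation rate is at most 0.7% in every cell.

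**4. Reading the table.** Two conditions are needed: breathing must differ by arm at the recording, and it must track response. With only the first, the a path is biased but the rate of false mediation stays at or below about 4%. The simulation stands in for the three-level model and bias-corrected bootstrap; it does not reproduce them. It also measures breathing without error and contains no true vagal effect, so it cannot show what adjustment would cost if such an effect existed.

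**The case against.** The strongest objection is that the premise comes from outside the documents. Section 6.2 says only that RSA occurs at the respiratory frequency and reflects parasympathetic control. It does not say that RSA changes with breathing when vagal tone is constant. That stands, so the dependence is treated here as an assumption with a range. The omission itself does not rest on it: breathing is recorded, differs by design in what the arms are taught, and is absent from the models.

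A reader might infer that yoga participants will show raised RSA and that the trial will find false vagal mediation. The documents do not support this. They report no breathing rates and no recording condition, and nothing shows that breathing will be slower at the ECG. The high rates in the table need several assumed effects together.

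A reader might also infer that a vagal claim should be allowed only if the pathway survives adjustment. Section 2.2 argues against this. It describes breathing regulation as reducing stress activation, with feedback possibly through the vagal system, so breathing may be an intended upstream step. Conditioning on it can remove a real effect. For the same reason the cortisol covariates are only a partial parallel: no arm trains smoking status or contraceptive use.

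Finally, mediation is the tertiary aim, and section 2.2 says only that the biomarkers may suggest pathways. That is right, and it limits the importance of the point.

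**Conclusion.** The concern holds in a limited form. As planned, the yoga vs SE path to vagal tone cannot separate a breathing change from a vagal one, so a positive result for Hypothesis 3.1 could be misattributed. Whether it would be depends on three things that the documents do not give: how strongly peak-valley RSA depends on breathing, whether breathing differs by arm at the recording, and whether breathing tracks response. Under the assumed ranges, false vagal mediation runs from about 0.5% to 78% without a breathing term and stays below 1% with one. These figures illustrate; they do not predict.

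The primary responder comparisons are untouched. This is a worthwhile, cheap improvement to tertiary Aim 3.

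The pre-ejection period mismatch is a separate wording inconsistency. A reader might take the Précis to name it as the vagal mediator. It is one of four possible mediators there, and the same paragraph goes on to predict mediation through vagal tone. The mismatch lends no weight to the breathing argument.

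**What to change.** In section 9.6, under the mediation analysis, pre-specify the following:

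- Extract breathing rate, and relative band amplitude if usable, from the existing respiration-band signal at baseline, week 6 and post-treatment. These are the RSA assessments that fall within the mediation model.
- Report breathing rate by arm at each of these assessments, and state the condition under which RSA is recorded.
- Report the RSA a path and the mediated pathway twice, without and with breathing as a time-varying covariate in both the RSA model and the response model. Label this a sensitivity analysis.
- Do not make the adjusted result a gate for the hypothesis, because breathing is changed by treatment and may lie on the causal path.
- If the pathway does not persist with breathing included, describe it as an RSA pathway not separable from breathing pattern, rather than as vagal tone.

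Separately, reconcile the mediator list in the Précis with section 9.5.2 and the schedule in 6.1.

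The cost is a few lines of SAP text and one or two more variables from a signal already recorded, provided that the trace is kept. The downside is that the adjusted estimate will be less precise and may remove a true vagal effect that acts through breathing. That is why both results should be shown. Fixing this before unblinding also prevents a later choice between them.
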